### **Work accomplished by PI**

*Reducing Barriers to living at home for the rural Veteran with Amyotrophic Lateral Sclerosis* (ORH N08-FY14Q4-S0-P01503, PI: [name]). This project consists of interviews with caregivers and Veterans with ALS about the challenges of living and the barriers to maintaining living at home. This study is currently ongoing, but preliminary results point to timely and appropriate access to care as an important feature. Communication and transportation issues also present as consistent themes.

*Increasing Access to pulmonary function testing for rural veterans with ALS through at home testing* (ORH FY 2015, PI: [name]). Begun in Oct 2014, this program provides in-home testing for forced vital capacity (FVC). FVC is an important measure in this study. Additionally, telehealth appointments will be available while the respiratory therapist is in the home to consult with other members of the ALS team. This program may provide important access to the population in this study.

"Machine Translation Divergences: A Formal Description and Proposed Solution," *Computational Linguistics*, 20:4, 1994. [name] was a NSF Presidential Faculty Fellow Awardee in 1997 for her seminal work on the problem of translating from one language into another in the face of *language divergences* (i.e., cross-linguistic distinctions). Her work resulted in a systematic solution to the divergence

problem based on the formalization of linguistically-motivated classes that facilitate the design and implementation of a language processing system that is general enough to be applied to problems in text processing, speech processing, and language translation.

Her subsequent research on cross-language divergence analysis for statistical word-level alignment (Dorr et al., 2002) was successful for analysis of both minimally divergent language pairs (Spanish and English) and maximally divergent language pairs (Spanish and Chinese). Her experience in studying divergent speech patterns will be extremely valuable in leading data analysis efforts of ALS patient speech at Florida IHMC.

### **Research Plan**

Population: Participants with ALS receiving medical services at James A. Haley Veterans' Hospital. According to the National VA ALS registry, one of the highest concentrations of Veterans with ALS is in Mid-Florida. In FY13, 136 Veterans with ALS were served by the Tampa VA. All veterans who meet inclusion criteria will be approached about the study.

Inclusion criteria: Veterans have been diagnosed with ALS, are native monolingual speakers of American English, have bulbar involvement identified during initial ALS inpatient evaluation, a forced vital capacity (FVC) of greater than 50% of the expected value for age, and an ALSFRS-R score of 40 or greater.

Exclusion criteria: a diagnosis of dementia, FVC less than 50%, inability to speak, or inability to follow directions.

Number of subjects: We will recruit 20 Veterans with ALS who currently have bulbar involvement into the study. The process of recruitment begins when potential recruits are initially assessed in the ALS clinic. The examining physician will make the potentially subject aware of the study. If the potential subject is interested, they will be referred to the research assistant, who will inform the subject about the study, and begin the consent process if the potential subject is interested in participating. 20 control healthy subjects without a diagnosed ALS will be recruited. A ONETIME recording will be done of the TIMIT and Ba repetition.

Timeline: Veterans will provide data quarterly (every 3 months) for two years for 8 visits total. Each time the Veteran visits the Tampa VA, the research assistant will make a set of voice recordings. If the Veteran is not able to come to the VA within a 3 month time period, the research assistant will make a home visit to make the recording. The control 20 healthy subjects without a diagnosed ALS will be a ONETIME recording of the TIMIT and Ba repetition.

Data Collected: In order to minimize the burden to the subjects, research data collection and clinical data collection is being coordinated. The following data is collected per standard of care each time the Veteran is seen

Potential participants will be screened and evaluated for *Amyotrophic lateral sclerosis* (or ALS) within the Tampa VA systems of care. After screening a letters will be mailed about the study to these potential participants. For those who respond to the letter showing interest in participating in the study and who are eligible, an appointment will be scheduled to meet for the consenting and enrollment process. There will be Waiver of document; for control 20 healthy subjects without a diagnosis of ALS. Script for waiver of Documentation will be used to recruit the 20 healthy subjects.

This information will be extracted by the Research Assistant from participants' medical records on a quarterly basis:

1. Forced Vital Capacity (FVC),
2. Penetration-Aspiration Scale (a paper-pencil screen; Rosenbek, 1996),
3. ALSFRS-R (Cedarbaum, 1999), and
4. Speech Intelligibility Test (SIT; Beukelman et al., 2007).
5. Ba repetition test ( Rong et al., 2015).

If any measurements are missing, the research assistant will confirm collection of clinical measurements and coordinate with the clinical team.

The research assistant will measure tongue strength using the Iowa Oral Performance Instrument (IOPI Medical, Redmond, WA), and speech recordings made of four preselected passages. These passages, selected from the Texas-Instrument/MIT (TIMIT) corpus (Garofolo et al., 1993), combat what would generally lead to unintelligibility in speech recognition by providing a "ground truth"; with the knowledge of what the sentence is in advance, even if the patient is not otherwise able to speak intelligibly, the speech recognition system can be appropriately calibrated to expect certain levels of deviation from a baseline. And, the 'Ba' repetition test ( Rong et al., 2015). The diadochokinetic (DDK) rate test in which the participants were asked to clearly and rapidly repeat /ba/ was used in (Rong et al. 2015), to help with speech intelligibility deterioration as a result neurologic atrophy. While this pilot study focuses on speech recognition that accommodates varying levels of impairment, in later stages of the disease, adaptive speech recognition technology would be most useful in combination with alternative and augmentative communication (AAC) technologies and brain computer interfaces (BCI); this powerful combination would accommodate typing, gaze, and head-mouse input, in addition to speech input (see related discussion in Dorr et al., 2015).

We would expect to follow a patient from enrollment to the end of the study, or end of life. When possible, speech recordings and assessments will be coordinated during the quarterly visits to Tampa VA. If not possible, separate visits will be scheduled. If the patient were unable to come to Tampa VA, home visits would be scheduled. If results are promising, we would seek additional funds to follow this cohort beyond the end of study.

The 20 control speakers will participate in ONETIME only, recording during the rest of the study time of the TIMIT Sentences and Ba repetition.

Participants diagnosed with ALS CPRS notes will be reviewed for the following co-existing conditions to be found on the CPRS Notes:

- I. Parkinson's disease
- II. Multiple Systems Atrophy
- III. Olivopontocerebellar degeneration
- IV. Shy Drager syndrome
- V. Progressive Supra nuclear palsy
- VI. Any kind of laryngeal dystonia

Data Analysis: Data analysis will be conducted at the Florida Institute of Human and Machine Cognition (IHMC) in Ocala, Florida. Data sharing and security will be governed under the IPA agreement between James A. Haley Veterans' Hospital and IHMC. Phonetic annotation of the training data is required in instances where we want to identify speech characteristics in the transcribed text (e.g., hypernasality). The Tampa VA will provide transcribed, annotated speech data (in addition to the audio recordings) to IHMC for setting up the baseline speech recognition system. To perform quality annotation, we will utilize a consistent set of guidelines to ensure that the system can learn patterns to aid in understanding speech with errors. Speech recordings will be separately annotated for speech irregularities by two research assistants using the annotation guidelines, and differences in annotations will be arbitrated by the PI or his designee. The annotated script, along with the original recording, will be de-identified and sent to IHMC using Cradeon, a FIPS 140-2 compliant encryption program. Sample annotations are provided below. It is critical that the degree to which the ALS has progressed be associated with each transcript, so that a different set of speech models can be produced for different degrees of ALS progression.

From the audio recordings collected, 90% will be used for training the system. A randomly selected 10% will be used to test the divergence construct.

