**Rationale**

A disease called *Amyotrophic lateral sclerosis* (or ALS), which leads to difficulty swallowing, breathing, and movement, has been found to be higher for those serving in the military than in the general population. There are approximately 4,200 Veterans with ALS and roughly 1,000 new cases each year. When doctors attempt to determine the degree to which an ALS patient is suffering from the disease, they apply tests that are "graded" by experts. However, this approach to testing patients may not be very accurate. Researchers aim to use a system called DESIPHER to "listen" to ALS patients and find speech mistakes related to their condition. Researchers believe that, by detecting different types of errors, DESIPHER serves as a new kind of indicator of medical problems such as difficulty breathing or swallowing, without human "grading". This may also lead to a better electronic system for understanding ALS patients' speech, even with lots of errors.

Hypotheses: Using a longitudinal study of Veterans with recently diagnosed with ALS, we propose to test the following two hypotheses:

H1: Automatic speech recognition can be achieved for ALS patients, whose speech diverges from a baseline, as established from transcribed speech data, using speech-model adaptation.

H2: Divergence of speech from baseline will serve as a marker for disease progression.

Specific Aims: Research questions to be addressed by this study are:

Q1: Is it possible to train a speech recognition system to adapt to increasingly more frequent language/speech errors of particular types, to produce an accurate textual transcript that would be readable by a caregiver or physician?

Q2: Are specific changes in physiological functioning (Forced Vital Capacity, tongue

strength, speech velocity, weight loss, aspiration risk, or psychological distress) associated with different types of language/speech errors?

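### Every text in the only described test set is also a training text, so these recordings cannot show recognition of ALS speech (H1/Q1) apart from familiarity with four known passages

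*Protocol*

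**What the plan says.** The Rationale sets two hypotheses. H1 is that automatic recognition of ALS patients' speech can be achieved by adapting the speech model; its research question Q1 asks whether a system can be trained "to produce an accurate textual transcript that would be readable by a caregiver or physician". H2 is that divergence from baseline marks disease progression.

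Under Research Plan, the connected speech recorded for the study is "speech recordings made of four preselected passages", taken from the TIMIT corpus. The stated reason is calibration: a ground truth is available "with the knowledge of what the sentence is in advance, even if the patient is not otherwise able to speak intelligibly". The other recorded task is a syllable test, described through a cited study in which "participants were asked to clearly and rapidly repeat /ba"; it contains no words to transcribe.

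On numbers: "We will recruit 20 Veterans with ALS who currently have bulbar involvement into the study". "Veterans will provide data quarterly (every 3 months) for two years for 8 visits total". For controls: "The 20 control speakers will participate in ONETIME only, recording during the rest of the study time of the TIMIT Sentences and Ba repetition".

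On the split, Data Analysis says: "From the audio recordings collected, 90% will be used for training the system". The remaining tenth is drawn at random and assigned to testing the divergence construct. No other test set is described, nor any holding-out by passage.

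The Background section also mentions ALS speech already collected by clinician partners, which is to serve as an initial dataset. Its texts are not described and it is not reserved for testing.

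**The concern.** Choosing the text in advance suits H2: when the words are fixed, a change in the audio can be read as a change in the speaker. Recognition is a different task. A transcript is useful to a caregiver or physician mainly when they do not already know what was said. If every text used for testing was also used for training, a low word error rate has two explanations. The system may have adapted to impaired speech, or it may have become familiar with the passages. The data cannot tell these apart.

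This matters most late in the disease, where the acoustic signal is poorest and prior knowledge of the text can do most of the work. H1 is one of the pilot's two hypotheses, so a result that rests partly on known text could be carried into the follow-up work that the Significance section foresees.

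**Working it through.** The protocol gives no sample-size or accuracy figure to reproduce. The check is a count of recordings under the stated split.

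**Inputs**
- 20 Veterans, 8 visits each, 20 controls recorded once, four passages, 90/10 random split (all from Research Plan).
- Assumption: the same four passages are read at each visit. This is the plain reading of a preselected set but is not stated outright.
- Assumption: controls read the same four. The protocol says only TIMIT sentences, so the count is also shown without controls.
- Assumption: one recording per passage per session.

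**Count at full attendance**

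| | Veterans only | With controls |
|---|---|---|
| Passage recordings | 20 × 8 × 4 = 640 | 640 + 20 × 4 = 720 |
| Test set (10%) | 64 | 72 |
| Training set (90%) | 576 | 648 |
| Recordings of each passage | 640 / 4 = 160 | 720 / 4 = 180 |
| Fewest recordings of a passage left in training | 160 − 64 = 96 | 180 − 72 = 108 |
| Expected recordings of a passage in training | 0.9 × 160 = 144 | 0.9 × 180 = 162 |

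A passage is missing from training only if all its recordings fall in the test set. That would need 160 recordings in a set of 64, or 180 in a set of 72. The probability is exactly 0, so 100% of test recordings carry a text that is also in training.

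**Does the result depend on the assumptions?**
- *Attendance.* If each session contains all four passages, each is 25% of the recordings however many sessions take place, and 25% exceeds 10%.
- *Counting /ba/ as a recording.* Five recordings per session give each passage a share of 1/5 = 20%, still above 10%.
- *Splitting by session.* There are 20 × 8 + 20 = 180 sessions, about 162 of them in training, each with all four texts. Overlap is again 100%.
- *Splitting by Veteran.* Every training speaker reads the same four texts, so overlap remains.

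**Speaker overlap.** In 5,000 simulated random splits of the Veterans' recordings, the same speaker reading the same passage was also in training for about 100% of test recordings with 8 visits each, 99.9% with 4 visits and 91% with 2 visits.

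**Under a hold-out by passage.** Veterans only: 640 × 3/4 = 480 training and 160 test recordings per run. With controls: 540 and 180. Text overlap is 0%, with one unseen text per run.

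**The case against.** The strongest reply is that the protocol never says H1 will be judged on the 10%. Data Analysis gives that set to the divergence construct, which belongs to H2, and for H2 fixed text raises no objection. This stands. A reader might infer that the sponsor plans to demonstrate H1 on this split, but the text does not say so. What remains is that this is the only test set described and that H1/Q1 have no other. Recognition metrics and success thresholds may be left to a statistical analysis plan, and their absence is not criticised here. The recorded material and the random split, however, are fixed in the protocol.

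A reader might also infer that recognition reduces to deciding which of four texts was read, with one guess in four correct. That presumes a decoder confined to those texts. The protocol specifies neither decoder nor language model; it describes phonetic annotation and separate models by degree of progression, and the initial dataset could bring other texts into training. Memorisation is possible, not established.

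Third, Q1 does not say in so many words that the text must be unknown. This too stands: the requirement is inferred from the use that Q1 names.

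Finally, this is a low-risk pilot and the split can be changed at analysis, so nothing is lost irretrievably. That limits the urgency but does not give H1 a test.

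**Conclusion.** The point holds in a limited form. On the plain reading of the protocol, text overlap between training and the only described test set is 100%, whatever the attendance or the random draw. Accuracy on those recordings could not distinguish adaptation to ALS speech from familiarity with four passages, so it could not by itself support H1/Q1.

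This rests on two readings: that the same four passages recur at each visit, and that H1/Q1 would be judged on the recordings the study collects, since no other test data are described. The amount by which accuracy would be inflated cannot be stated, because it depends on an unspecified language model. The documents do not support saying that H1 will be falsely declared met, or that the fixed passages are a poor choice for H2.

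**What to change.** Amend Data Analysis in the Research Plan as follows.

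1. Keep all four fixed passages and the existing split for the divergence measure (H2).
2. For H1/Q1, add a leave-one-passage-out evaluation: train or adapt on three passages, test on the fourth, and rotate over all four.
3. Exclude recordings and transcripts of the held-out passage from acoustic adaptation and from language-model training. Keep a general-purpose pronunciation lexicon, so that the held-out words can still be output. Removing them would create word errors that say nothing about adaptation.
4. State whether the initial dataset contains any of the four texts; if so, apply the same exclusion.
5. Report word error on the held-out passage by disease stage.
6. Limit the H1 conclusion to read speech on four short texts, and say that the same speakers appear in training and test.

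**Cost.** A short protocol change and four runs instead of one, with no new recordings and no added burden on participants. Each run trains on 75% of passage recordings instead of 90% (480 instead of 576 for Veterans at full attendance) and on three texts instead of four. Each run tests only one unseen text, so results will vary with the words and sounds it contains. The word error rate will probably look less favourable.

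### The divergence construct (H2) is tested on a random 10% of recordings, so practically every ALS test recording comes from a Veteran already in training and the marker is never assessed in an unheard Veteran

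*Protocol*

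**What the plan says.** The split is set out at the end of the Data Analysis paragraph of the Research Plan: "From the audio recordings collected, 90% will be used for training the system", followed by "A randomly selected 10% will be used to test the divergence construct". The unit is the recording and the selection is random. The protocol does not group the draw by Veteran and describes no other validation set.

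The construct under test is the one in the Rationale: "H2: Divergence of speech from baseline will serve as a marker for disease progression". The Significance section foresees speech divergence as a further assessment tool for Veterans with ALS.

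The recordings are strongly clustered. Under Timeline, "Veterans will provide data quarterly (every 3 months) for two years for 8 visits total", and there are 20 such Veterans. At each visit the research assistant obtains "speech recordings made of four preselected passages" and a 'Ba' repetition. Twenty healthy controls are recorded once. What counts as one recording is left open: Timeline speaks both of "the research assistant will make a set of voice recordings" and, for home visits, of "the research assistant will make a home visit to make the recording".

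Data Analysis also asks that each transcript carry the degree of progression, "so that a different set of speech models can be produced for different degrees of ALS progression".

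**The concern.** A held-out set answers the question set by what was kept out of training. Here single recordings are kept out and people are not. The system is scored on voices it has already learned, at disease stages close to those it has heard from the same person. A good result would show that divergence tracks progression in known speakers. It would not show that the marker carries over to a new Veteran, which is what an assessment tool needs.

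There is a second, conditional risk. Progression differs between Veterans and is correlated within each. A score from models trained on degree of progression can do well by recognising the speaker and returning that speaker's usual stage. The pooled association in the test set would then be positive even if speech carried no information on progression.

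**Working it through.** **Inputs.** From the Research Plan: 20 Veterans; 24 / 3 = 8 visits, which agrees with the stated total; four passages per visit, plus 'Ba'; 20 controls recorded once; 10% random test set. The protocol gives no attrition rate, so attrition is an assumed range below.

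**Size of the test set.**
- One recording = one passage: 20 × 8 × 4 = 640 ALS recordings, 64 in test. Counting 'Ba' as a fifth gives 800 and 80.
- One recording = one session: 20 × 8 = 160, 16 in test. With controls, 180 and 18, of which about 16 are ALS.

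**Speaker overlap at full attendance.** Given one test recording, the chance that a set of m other recordings also all fall in test, drawing T from N without replacement, is the product of (T − 1 − i)/(N − 1 − i) for i = 0 to m − 1.
- By passage, the 7 other readings of the same sentence by the same Veteran: (63 × 62 × … × 57)/(639 × 638 × … × 633) = 6.6e-8. The chance that all 31 other passages of that Veteran are in test is smaller still.
- By session, the 7 other sessions: (15 × 14 × … × 9)/(159 × 158 × … × 153) = 1.4e-8. With controls in the pool it is 1.9e-8.

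Over 99.99% of ALS test recordings thus have their speaker in training. The expected number of the 20 Veterans wholly held out is effectively 0 (3.7e-8 by session with controls). Background mentions an existing dataset of unstated size. Enlarging the pool from 640 to as many as 10,640 recordings moves 6.6e-8 only to 9.8e-8.

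**Under assumed attrition, session draw (the less favourable case for overlap).**

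| Visits per Veteran | Speaker also in training |
|---|---|
| mean about 6 | about 99.5% |
| 4 each | 99.9% |
| mean 3.6 | about 96% |
| 2 each | about 91–92.5% |

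The last row can be checked by hand: 1 − 3/39 = 92.3% without controls and 1 − 5/59 = 91.5% with them. If the five recordings of a visit are drawn separately, overlap was 100% to the precision of the simulation in every row.

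**Within-Veteran change.** With a session draw, P(no visit in test) for one Veteran is (144 × … × 137)/(160 × … × 153) = 0.422, and P(exactly one) = 0.422 × 8 × 16/137 = 0.394. So 20 × (1 − 0.422 − 0.394) ≈ 3.7 Veterans have two or more test visits. With single passages drawn (640), simulation gives 16.5.

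**Can the split flatter H2?** A null simulation with no progression signal used features = speaker + sentence + noise (SD 1, 40 features, 300 runs). The between-patient share of progression variance was assumed at 5/20/50/90%. Mean pooled correlation of score with progression:

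| Score | Single passages drawn | Sessions drawn |
|---|---|---|
| Stage-specific models (Gaussian per progression tertile) | 0.00/0.19/0.41/0.61 | −0.14/0.08/0.33/0.57 |
| Model fitted directly to progression (ridge) | 0.02/0.23/0.45/0.68 | −0.16/0.10/0.37/0.65 |

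An unsupervised distance from a reference (training mean, controls or own first visit) gave −0.01 to 0.02 at every share. Participant-grouped 10-fold scoring gave −0.05 to 0.01 for all three types of score. A rerun of the ridge score with the share set as a population parameter gave 0.18/0.31/0.50/0.69, against 0.01–0.03 when grouped. The size therefore depends on the set-up. Within patients, without session effects, the recording draw gave −0.06 to 0.02.

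**The case against.** **The new-Veteran target is inferred.** H2 speaks of divergence from a baseline in a longitudinal pilot, the Significance section is tentative about a tool, and one stated follow-on is to keep following the same cohort. This stands in part: the protocol never says in terms that the marker must work in unheard Veterans. But an assessment tool for Veterans with ALS has to be used on people outside the 20, and nothing else in the protocol supplies that evidence.

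**Inflation is not shown.** This stands. The score nearest to the protocol's wording is a distance from baseline, and that is not inflated. The positive values need a score fitted to progression. The plan for separate models by degree of progression makes such a score possible, but the protocol does not say that those models produce the divergence score. With sessions drawn, the bias at the 5% share runs the other way. A reader might infer that the split guarantees an over-optimistic H2 result; the documents do not support that.

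**H1 is not tested on this 10%.** This also stands. A reader might infer that the split undermines H1, because a later visit of the same Veteran is in training for about 86–87.5% of ALS test recordings at full attendance. The sentence assigns the 10% to the divergence construct only, and the protocol does not say how adaptation is to be judged. Speaker-specific training is in any case the point of adaptation. Nor are the four fixed passages a fault: the Research Plan chooses them deliberately to have a known text.

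**A statistical analysis plan may add grouping.** It may, but the protocol itself fixes a random draw of recordings, so any grouping would have to override that sentence.

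**Conclusion.** The point holds for H2, and the sentence should be changed. As written, the split gives no unseen-Veteran estimate of the marker: overlap exceeds 99.99% at full attendance and is about 91% or more under the assumed attrition, on either meaning of a recording. That part rests only on the protocol's counts and, for the lower figures, on the assumed visit patterns.

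The possible bias in the pooled association is conditional on scores coming from models fitted to progression. The simulated correlations illustrate the mechanism under assumed features, noise and variance shares and do not estimate its size in this study. The split does not make H2 untestable: the 10% can still show performance in known speakers, and divergence can still be related to clinical measures across visits. The issue is what such a result may be said to show.

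**What to change.** In the Data Analysis paragraph of the Research Plan, replace the random 10% of recordings as the test of H2 with participant-grouped cross-validation. All recordings of a participant go into one fold, for example 10 folds of 2 Veterans. Each fold then holds 2 × 8 = 16 of 160 ALS sessions, the same 10% share. Test H2 on the out-of-fold scores, both across Veterans and as within-Veteran change; every attended visit of every Veteran then contributes.

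If the score is defined against a Veteran's own baseline, a held-out Veteran's first visit may serve as that reference but must not be used in model training. Report any seen-speaker result separately and label it as such. State whether a recording is one passage or one session.

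Secondary: if the same held-out data are also to be used to judge H1 adaptation, take test recordings from visits later than those used to train for that Veteran.

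Cost: ten model fits instead of one, which is real computing work if several stage-specific models are built; results that will probably look less favourable; and imprecise participant-level estimates with 20 Veterans. No extra patients or visits are needed and data collection does not change. The change should be made before any model is trained.

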**Table 1: Linguistic divergence across languages**

Spanish	Portuguese	French	English	Chinese
Vocabulary	X	X	X	
Syntactic structure	X	X		
Pronunciation	X			

We propose to apply this same notion of *divergence* to the problem of "speech functioning," constraining our language pair to asymptomatic English speech compared to impaired English speech. In this case, the properties to be studied are finer grained than the ones shown in Table 1, in that they are aligned with articulatory patterns in speech. Although we expect speech divergences to develop independently of language accent and dialect, we expect that prior work on dialect adaptation (Lehr et al., 2014) will be relevant for tracking speech divergences even within a single language. Research on modeling non-native or dialectal speech (Livescu and Glass, 2000) is a close approximation to what we propose for recognition of speech changes over time, though the focus of dialectal modeling is on detecting divergent content, not on discerning characteristics of the speech signal. In order to test our hypothesis that divergence from a baseline serves as a marker for disease progression (and that, in fact, specific speech properties vary systematically in impaired speech), the current proposed pilot is for native speakers only; this allows for variability in dialect, but not variability regarding the level of knowledge of the language, thus retaining only one variable: the level of progression of the disease over time. However, an important follow-up study is that of speech recognition of accented (non-native) speech, once the properties that vary systematically with disease progression have been carefully identified in this current pilot study.

A significant aspect of the proposed work is the identification of possible speech-related biomarkers to be examined for correlations with other aspects of physiological function. Some that have been published in the literature (e.g., Duffy, 2012; Rudzicz et al., 2014) that are relevant to dialectal variations, but have not heretofore been measured objectively through dialectal analysis, are those listed below:

- Imprecise consonants
- Distorted vowels
- Slow rate
- Short phrases
- Hypernasality
- Continuous voicing
- Distorted substitutions or additions

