Table 2 is a notional table illustrating a range of articulatory properties for "baseline" English (as determined for a native English speaker who has no speech impairment, i.e. pre-symptomatic) compared to those exhibited during different stages of ALS—early, mid, late—thus providing a framework for capturing the degree of divergence. The final column has the highest level of divergence from the baseline: imprecise consonants, distorted vowels, and continuous bilabials.

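### Testing divergence on a random 10% of recordings keeps most of each Veteran's quarterly series out of the stated test and puts the same speakers in training and test

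*Protocol*

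**What the plan says.** The Rationale introduces both hypotheses with the words "Using a longitudinal study of Veterans with recently diagnosed with ALS". H1 concerns whether automatic recognition can be achieved by adapting speech models. H2 reads: "Divergence of speech from baseline will serve as a marker for disease progression". The Background, after Table 1, describes the design as "thus retaining only one variable: the level of progression of the disease over time".

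The Research Plan sets 20 Veterans with quarterly visits over two years, 8 in all, and 20 healthy controls. On the controls it says: "The 20 control speakers will participate in ONETIME only".

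The Data Analysis paragraph then fixes how recordings are used: "From the audio recordings collected, 90% will be used for training the system", followed by "A randomly selected 10% will be used to test the divergence construct". It describes no other data set for testing divergence. It states no stratification by visit or disease stage, no grouping by speaker, and no unit for a recording.

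The Research Plan's wording on the unit goes both ways. The Timeline has a visit produce a set of recordings, and the data-collection text speaks of recordings of four reading passages. Yet the home-visit sentence and the control sentences use the singular for a whole session.

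**The concern.** H2 is a statement about change over time. The evidence for it is the run of quarterly visits in the same Veteran. A simple random 10% of recordings is a usual way to hold out data for checking a recogniser, but it suits a longitudinal hypothesis poorly. It spreads a small test sample over 20 Veterans and 8 visits without regard to who spoke or when.

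Two things are at stake. First, most of the visits planned to show divergence moving with progression would not be used in the only divergence test that the Protocol describes. Second, nearly every tested Veteran would also have supplied training recordings. A trained scorer would then be judged on speakers it has already learned, which says little about how it would mark progression in a new patient.

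**Working it through.** The Protocol gives no test-set count of its own, so there is no figure to reproduce. The counts below follow from its design numbers.

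**Inputs (Research Plan).** 20 Veterans, 8 visits each; 20 controls, one session each; test share 10%, drawn at random. Assumptions: all visits attended (the favourable case), and controls included in the pool.

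**Unit = session**
- Pool: 20 × 8 + 20 × 1 = 180. Test set: 0.10 × 180 = 18.
- Expected Veteran sessions in the test: 18 × 160/180 = 16.
- Test sessions per Veteran are hypergeometric: P(X = k) = C(8,k) × C(172,18−k) / C(180,18).
- P(0) = 0.423, P(1) = 0.393, P(2 or more) = 0.184.
- Over 20 Veterans: about 8.5 have no test visit, 7.9 have one, and 3.7 have two or more (95% simulation range 2 to 6), of whom about 0.7 have three or more.
- Average visits represented: 0.10 × 8 = 0.8 of 8.
- Without controls in the pool (16 of 160 drawn), Veterans with two or more: 3.7. The result does not depend on how controls are handled.
- With 6 completed visits per Veteran: 2.2. With 4: 1.0.

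**Unit = single passage or task** (4 files per session for the reading passages, or 5 with the Ba task; the number of files is an assumption)
- 4 files: pool 180 × 4 = 720, test 72, of which about 64 are Veteran files.
- 5 files: pool 180 × 5 = 900, test 90, of which about 80 are Veteran files.
- Chance that a given visit has at least one test file is about 1 − 0.9^4 = 0.344 or 1 − 0.9^5 = 0.410.
- Visits represented per Veteran: 8 × 0.344 = 2.8 or 8 × 0.410 = 3.3.
- Veterans with two or more test visits, by simulation: 16.6 (4 files) or 18.2 (5 files). Binomial check: 20 × [1 − 0.656^8 − 8 × 0.344 × 0.656^7] = 16.4, and 18.1 for 5 files.

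| | Session | Single passage or task |
|---|---|---|
| Veteran recordings tested | about 16 | about 64 to 80 |
| Veterans with two or more test visits | about 3.7 of 20 | about 17 to 18 of 20 |
| Visits represented per Veteran | 0.8 of 8 | about 2.8 to 3.3 of 8 |

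**Speaker overlap.** A Veteran with 8 sessions is absent from training only if all 8 fall in the test. That has a chance of about 0.1^8, or 1 in 100 million, by session, and less by file. In practice every tested Veteran with a full series is also a training speaker.

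**The case against.** **The link to H2 is an inference.** The Data Analysis paragraph does not name H2. Its surrounding text is about building the recogniser, so the 90/10 split could be ordinary model validation. H1 also speaks of divergence from a baseline. Nothing says that the association with physiological measures (research question Q2) is confined to the 10%, and a SAP, which was not available, could set that analysis. This stands as a caution. H2 remains the better reading, because the Rationale and Background tie divergence from baseline to progression and no other data set is given for testing it.

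**The unit is open.** A reader might infer that only about 4 of 20 Veterans contribute repeat visits. That holds only if a recording is a session, and the Research Plan supports both units. With single tasks, the scarcity of Veterans with repeat visits largely disappears. What remains is that fewer than half of the visits are represented.

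Three stronger readings are tempting but not supported:
- *Few controls in the test set means the baseline is lost.* By session about 18 × 20/180 = 2 controls are expected there. But H1 establishes the baseline from transcribed speech, and a baseline model would be learned from the training share, which would hold the other 18 or so.
- *Dialect confounds the test.* The Background says of restricting to native speakers that "this allows for variability in dialect, but not variability regarding the level of knowledge of the language", but it also states an expectation that divergence develops independently of accent and dialect. The point does not need the dialect argument.
- *The rule is what makes the result imprecise.* At a correlation of 0.5, 16 independent recordings give a 95% interval of 0.01 to 0.80, and one recording from each of 20 Veterans gives 0.07 to 0.77. The width mainly reflects a 20-Veteran pilot, and the Protocol specifies no correlation test.

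**Conclusion.** The point holds in this form: the stated rule for testing divergence does not fit a longitudinal hypothesis. Under either unit most of the planned series stays out of the stated test, with on average 0.8 of 8 visits per Veteran represented by session, or about 2.8 to 3.3 of 8 by task. The random split also places the same speakers in training and test.

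This rests on reading the divergence construct as H2, on full attendance (missed visits or deaths lower the session counts), and on 4 or 5 files per session for the task-level figures. It does not show that H2 cannot be tested with these data. The recordings will exist, and only the allocation rule holds them back. The Protocol should be changed, but the study design need not be.

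**What to change.** In the Data Analysis paragraph of the Research Plan:

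1. Limit the random 90/10 split to recogniser accuracy (H1), and state whether a recording is a session or a single passage or task.
2. For H2, state that divergence is scored in every Veteran recording at every visit and analysed as change within Veteran over visits.
3. State that any trained scorer is built without the recordings of the Veteran being scored (leave one Veteran out).

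The cost is Protocol wording, with no new patients, visits or recordings. If a trained model does the scoring, up to 20 refits are needed instead of one, and the scoring systems will differ slightly between Veterans.
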